6.5 POOLING OF CENTRES

This section is not applicable, because the study was performed in only one centre.

6.6 HANDLING OF MISSING DATA AND OUTLIERS

Data of screened subjects who were withdrawn from the trial prior to first administration of any study drug will not be reported in the CTR.

Data of subjects who failed to complete all periods of the study (dropouts or withdrawals) will be reported in the CTR as far as their data are available. All withdrawals will be documented and the reason for withdrawal recorded in the CTR.

CTP: *With respect to safety evaluations, it is not planned to impute missing values.*

The only exception where imputation might be necessary for safety evaluation are AE dates. Missing or incomplete AE dates are imputed according to BI standards (4) [001-MCG-156_RD-01].

Missing data and outliers of PK data are handled according to BI standards (5).

Blood/ Plasma/ Urine/ Faeces drug concentration or [¹⁴C]-radioactivity-time profiles

CTP: *Drug concentration data identified with NOS (no sample available), NOR (no valid result), NOA (not analysed), BLQ (below the lower limit of quantification), or NOP (no peak detectable) will be displayed as such and not replaced by zero at any time point (this rule also applies also to the lag phase, including the predose values).*

Pharmacokinetic parameters

CTP: *For the non-compartmental analysis, concentration data identified with NOS, NOR or NOA will generally not be considered. Concentration values in the lag phase identified as BLQ or NOP will be set to zero. All other BLQ/NOP values of the profile will be ignored. The lag phase is defined as the period between time zero and the first time point with a concentration above the quantification limit.*

6.7 BASELINE, TIME WINDOWS AND CALCULATED VISITS

The last non-missing value determined prior to the first study drug administration will be defined as baseline.

Time windows are defined in Section 6.1 of the CTP. Adherence to time windows will be checked at the RPM/DBLM.

7. PLANNED ANALYSIS

The format of the listings and tables will follow the BI guideline "Reporting of clinical trials and project summaries" (6).

The individual values of all subjects will be listed, sorted by dose group, subject number and visit. AE listings will be sorted by assigned treatment (see [Section 7.8.1](#) below for details). The listings will be contained in Appendix 16.2 (SDL) of the CTR.

The following standard descriptive statistical parameters will be displayed in summary tables of continuous variables:

N	number of non-missing observations
Mean	arithmetic mean
SD	standard deviation
Min	minimum
Median	median
Max	maximum

For plasma concentrations as well as for all PK parameters, the following descriptive statistics will additionally be calculated:

CV	arithmetic coefficient of variation
gMean	geometric mean
gCV	geometric coefficient of variation

The data format for descriptive statistics of plasma concentrations will be identical with the data format of the respective concentrations. The descriptive statistics of PK parameters will be calculated using the individual values with the number of decimal places as provided by the evaluation program. Then the individual values as well as the descriptive statistics will be reported with three significant digits in the CTR.

Tabulations of frequencies for categorical data will include all possible categories and will display the number of observations in a category as well as the percentage (%) relative to the respective treatment. Percentages will be rounded to one decimal place. The category missing will be displayed if and only if there actually are missing values. Percentages will be based on all subjects in the respective subject set whether they have non-missing values or not.

7.1 DEMOGRAPHIC AND OTHER BASELINE CHARACTERISTICS

Only descriptive statistics are planned for this section of the report. These will be based on the TS.

7.2 CONCOMITANT DISEASES AND MEDICATION

Concomitant diseases will be coded according to MedDRA, version 21.1. Concomitant medication will be coded according to the World Health Organisation – Drug Dictionary, version of March 2018.

Only descriptive statistics are planned for this section of the report.

A medication will be considered concomitant to a dose group, if it

- is ongoing at the time of first administration of this treatment, or
- starts within the analysis phase of the respective treatment (see [Section 6.1](#) for a definition of treatments and analysis phases).

7.3 TREATMENT COMPLIANCE

Treatment compliance will not be analysed as a specific endpoint (cf. [Section 5.4.2](#)). Any deviations from complete intake will be addressed in the RPM/DBLM (cf. [Section 6.2](#)) and described in the CTR.

7.4 PRIMARY ENDPOINTS

Only descriptive statistics are planned for this section of the CTR. These will be based on the PKS. The analysis of standard PK parameters is performed according to BI standards ([5](#)) [001-MCS-36-472_RD-01].

Exclusion of PK parameters

The ADS ADPP contains column variables APEXC and APEXCO indicating inclusion/exclusion (APEXC) of a PK parameter and an analysis flag comment (APEXCO). All analyses based on the PKS are based on PK parameter values which are not flagged for exclusion, i.e. with APEXC equal to "Included".

Exclusion of plasma/urine concentrations

The ADS ADPC (PK concentrations per time-point or per time-interval) contains column variables ACEXC or ACEXCO indicating inclusion/exclusion (ACEXC) of a concentration and an analysis flag comment (ACEXCO). Exclusion of a concentration depends on the analysis flag comment ACEXCO. For example, if ACEXCO is set to "ALL CALC", the value will be excluded for all types of analyses based on concentrations. If ACEXCO is set to "DESC STATS" the value will be excluded from descriptive evaluations per planned time point/time interval. If ACEXCO contains the addition "TIME VIOLATION" or "TIME DEVIATION", the value can be used for further analyses based on actual times. If ACEXCO is set to "HALF LIFE", the value will be excluded from half-life calculation only; the value is included for all other analyses. Excluded concentration itself will be listed in the CTR associated with an appropriate flag.

Further details are given in "Noncompartmental Pharmacokinetic / Pharmacodynamic Analyses of Clinical Studies" ([5](#)) and "Description of Analytical Transfer Files and PK/PD Data Files" ([7](#)).

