3.3.5 Replacement of subjects

In case a subject vomits within 8 h after trial drug administration assuming an incomplete absorption of the radiolabelled compound an additional subject may be entered and dosed to ensure that 6 evaluable subjects will complete the study as per protocol.

Proprietary confidential information © 2018 Boehringer Ingelheim International GmbH or one or more of its affiliated companies

In case some subjects do not complete the trial, the trial clinical monitor together with the trial pharmacokineticist and the trial statistician are to decide if and how many subjects will be replaced. Replacement of subjects and dosing of additional subjects as described above should always be done in mutual agreement with the principal investigator. A replacement subject will be assigned a unique study subject number.

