4.1.4 Drug assignment and administration of doses for each subject

In the morning of Day 1, following an overnight fast of at least 10 h, all subjects will receive one single dose of the trial drug (BI 730357 BS (C-14) oral solution 5 mg/mL (10 mL; 3.7 MBq)).

The medication will be administered as a single oral dose together with 240 mL of water to a subject in the sitting position under supervision of the investigator or an authorised designee. After administration, will determine for each volunteer the residual amount of [¹⁴C]-radioactivity in the syringe used for administration. The amount of administered radiolabelled medication will be calculated based on pre- and post-dose weight of the syringe used for oral administration.

The so-called four-eye principle (two-person rule) should be applied for administration of trial medication.

During the first 4 h after drug administration, subjects are not allowed to lie down (i.e., no declination of the upper body of more than 45 degrees from upright posture) except for medical examination or if necessary for any medical reasons (e.g. adverse events). For restrictions with regard to diet and fluid intake see [Section 4.2.2.2](#).

After drug administration subjects will be kept under close medical surveillance until planned discharge from the unit on Day 15. In case release criteria for radioactivity recovery have not been met on Day 15, subjects will come back to the unit for up to five once-weekly 24 h sampling periods until discharge criteria are met or after the last collection interval Day 49-50 was completed (see [Section 3.1](#)).

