5.5.2.7 Collection of vomit

If vomiting occurs in a volunteer within 12 h after drug administration, the vomit will be collected for determination of weight and [¹⁴C]-radioactivity.

For a detailed description of vomit sampling, sample preparation, sample storage, labelling, and sample shipment refer to the laboratory manual.

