5.5.3.3 Radiokinetic and Excretion Balance

Determination of [¹⁴C]-radioactivity concentrations in plasma, whole blood, urine, and faeces (and vomit, if applicable) will be done by means of validated liquid scintillation counting methods at

The blood, plasma, urine and faeces concentrations of radioactivity will be determined in agreement with relevant Standard Operating Procedures (SOPs).

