7.3 PLANNED ANALYSES

Adherence to the protocol (such as inclusion/exclusion criteria, times of measurement, compliance with intake of trial medication, treatment dispensing errors, prohibited concomitant medication, completeness and consistency of data) will be checked. Important protocol deviations (iPDs) will be identified no later than in the Report Planning Meeting and provided in the TSAP.

Plasma/urine/faeces concentration data and parameters of a subject will be included in the statistical pharmacokinetic (PK) analyses if they are not flagged for exclusion due to a protocol deviation relevant to the evaluation of PK (to be decided no later than in the Report

Proprietary confidential information © 2018 Boehringer Ingelheim International GmbH or one or more of its affiliated companies

Planning Meeting) or due to PK non-evaluability (as revealed during data analysis, based on the criteria specified below). Exclusion of a subject's data will be documented in the CTR.

Relevant protocol deviations may be:

- Incorrect trial medication taken, i.e. the subject received at least one dose of trial medication the subject was not assigned to
- Incorrect dose of trial medication taken
- Use of restricted medications

Plasma, urine and faeces concentrations and/or parameters will be considered as non-evaluable, if for example

- a pre-dose concentration >5% of the C_{max} value of that subject
- missing samples/concentration data at important phases of PK disposition curve

The following subject and analysis sets will be defined for this trial:

Treated set (TS):

This subject set includes all subjects who were documented to have received one dose of study drug. This is the full analysis set population in the sense of ICH-E9.

PK analysis set (PKS):

The PK analysis set includes all subjects in the treated set who provide at least one value for primary or secondary PK endpoint and are not excluded according to the description above. Thus, a subject will be included in the PKS, even if he contributes only one PK endpoint value for the statistical assessment.

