5. ENDPOINTS

5.1 PRIMARY ENDPOINTS

Primary endpoints are PK endpoints of mass balance recovery of [¹⁴C]-radioactivity as defined in Section 5.5.1.1 of the CTP:

- $fe_{urine, 0-t_2}$ (fraction of [¹⁴C]-radioactivity excreted in urine as percentage of the administered dose over the time interval from 0 to t_2 (where t_2 is the last quantifiable data point across all subjects))
- $fe_{faeces, 0-t_2}$ (fraction of [¹⁴C]-radioactivity excreted in faeces as percentage of the administered dose over the time interval from 0 to t_2 (where t_2 is the last quantifiable data point across all subjects))

CTP: Timeframe: *The timeframe for determination of these endpoints depends on excretion/recovery of radioactivity and may vary between 2-7 weeks, inclusive, after drug administration.*

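### Does the analysis plan need an explicit rule for the primary recovery values of a subject who vomits after dosing?

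*SAP*

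**What the plan says.** **Replacement.** If a subject vomits within 8 h of dosing, Protocol 3.3.5 provides that "an additional subject may be entered and dosed to ensure that 6 evaluable subjects will complete the study as per protocol". Both 3.3 and 3.3.5 tie this to presumed incomplete absorption. The synopsis and 3.3 cap the number entered at 8.

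**Analysis set.** Protocol 7.3 places in the PK set (PKS) every treated subject with at least one primary or secondary PK value who has not been excluded: "Thus, a subject will be included in the PKS, even if he contributes only one PK endpoint value for the statistical assessment". Exclusion can follow from a PK-relevant protocol deviation or from non-evaluability. The latter is introduced by the words "concentrations and/or parameters will be considered as non-evaluable, if for example" and illustrated by a high pre-dose concentration and by missing samples. Vomiting is not among the examples.

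**Mechanism.** SAP 7.4 defines an inclusion/exclusion flag (APEXC) and a comment field for each PK parameter: "All analyses based on the PKS are based on PK parameter values which are not flagged for exclusion". SAP 6.3 sends exceptional cases and set allocation to the report planning meeting. Protocol 7.3 requires exclusions to be documented in the trial report, and 7.3.5 has excluded subjects reported with their individual values.

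**Dose and vomit.** Faecal fe is the radioactivity "excreted in faeces as percentage of the administered dose over the time interval from 0 to" the last quantifiable point (SAP 5.1); urinary fe is defined in the same way. Protocol 4.1.4 gives the dose: "The amount of administered radiolabelled medication will be calculated based on pre- and post-dose weight of the syringe used for oral administration". Protocol 5.5.2.7 adds: "If vomiting occurs in a volunteer within 12 h after drug administration, the vomit will be collected for determination of weight" and radioactivity, and 5.5.3.3 confirms that counting in plasma, whole blood, urine "and faeces (and vomit, if applicable) will be done by means of validated liquid scintillation counting methods".

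**The concern.** The plan expects that vomiting may happen: Protocol 7.6 names it among the reasons for the sample size. It sets out replacement and measurement of vomit, yet the visible analysis text never mentions vomiting.

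Two things look open. First, replacing a subject implies that he is not evaluable, but the PKS rule read alone would keep him, because one endpoint value is enough. The primary table could then show N = 6 or N = 7. Second, activity lost in vomit stays in the denominator of fe and reaches neither urine nor faeces, so an uncorrected fe can only be lower. No sentence says whether the vomit count adjusts the dose or is only reported. The second point is sharpest at 8 to 12 h, where vomit is collected but the replacement rule does not apply, so nothing marks the subject as non-evaluable.

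With six to eight subjects, one low value can visibly move the mean and SD of the primary endpoint, and the decision may come at a meeting where recoveries are already known.

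**Working it through.** The documents give no figure to reproduce; Protocol 7.6 states that no precision or power calculation was made. The check therefore has a textual part and an illustration.

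**Text, question by question**

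| Question | What the plan supplies |
|---|---|
| Is a subject replaced for vomiting meant to count? | Replacement aims at six evaluable subjects and presumes incomplete absorption (Protocol 3.3.5), so the intent is to leave him out |
| Can his value be left out? | Yes: the non-evaluability list is only illustrative (Protocol 7.3), and SAP 7.4 flags single parameters |
| Who decides? | The report planning meeting (SAP 6.3); SAP 6.2 also lets the deviation table be extended |
| Is the exclusion visible? | Yes: documented (Protocol 7.3), with individual values reported (7.3.5) |
| Which dose is the denominator? | The syringe-weight dose (Protocol 4.1.4); no other dose appears |
| Where does vomit enter fe? | Nowhere: fe is defined for urine and faeces only, and vomit is a separately measured matrix |

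Only the sentence linking the first row to the second is missing. The last two rows are a literal reading of the definitions, not a stated rule.

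**Illustration**

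Inputs: total recovery of 90% (the release threshold in Protocol 3.1), split 86:14 between faeces and urine (the dosimetry assumption in Appendix 10.1). This gives faeces 0.86 × 90 = 77.4% and urine 0.14 × 90 = 12.6%. Assumed here, not taken from the documents: CVs of 5% and 15%, and every vomited fraction L. The six values are 77.4 × (1 + 0.05z) and 12.6 × (1 + 0.15z), with z = (−1.5, −0.75, 0, 0, 0.75, 1.5) rescaled to SD 1. For faeces: mean 77.4, SD 3.9.

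*A. A seventh subject vomits within 8 h and is kept on the syringe dose.* His faecal value is 77.4(1 − L), so the mean is 77.4(1 − L/7).

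| L | Faeces mean | SD | Geometric mean | Urine mean |
|---|---|---|---|---|
| Excluded (N = 6) | 77.4 | 3.9 | – | 12.6 |
| 10% (N = 7) | 76.3 | 4.6 | 76.2 | 12.4 |
| 30% (N = 7) | 74.1 | 9.5 | 73.5 | 12.1 |
| 50% (N = 7) | 71.9 | 15.0 | 70.0 | 11.7 |

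Dividing his value by dose minus vomit instead would give 77.4 (SD 3.5). The median stays at 77.4 throughout, but only because two z values were set to exactly 0.

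*B. One of the six, a central one, vomits at 8 to 12 h.* The mean is 77.4(1 − L/6), and his urine-plus-faeces total is 90(1 − L).

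| L | His total | Faeces mean | SD | Median |
|---|---|---|---|---|
| 1% | 89.1 | 77.3 | 3.9 | 77.0 |
| 5% | 85.5 | 76.8 | 4.2 | 76.0 |
| 10% | 81.0 | 76.1 | 5.0 | 76.0 |

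The mean falls by at most 77.4 − 76.1 = 1.3 points. Here the median falls too, by up to 1.4 points, so it is no safeguard in this case.

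*Two subjects who vomit (N = 8).* With total recoveries of 86, 88, 90, 90, 92 and 94% (mean 90.0, SD 2.8), adding two subjects who each lost half the dose gives values of 45% for each, and (540 + 90)/8 = 78.8, SD 21.0. Leaving them out returns 90.0.

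**The case for a change.** The strongest case for a change is that the remedy is cheap and the default reading is awkward. Two sentences in SAP 7.4 would settle both points, and the flag and the vomit counts already exist. Read strictly, SAP 6.3 ties PKS exclusion to PK-relevant important deviations. Vomiting is not in the deviation table and is not itself a breach of protocol, so a literal analyst could keep the subject, against the purpose of replacing him. SAP 7.3 sends departures from complete intake to the meeting, but someone who swallowed everything and then vomited is not plainly such a case.

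It stands that no visible sentence names vomiting as a reason to set the flag, and that fe is lower for any subject who vomits and is kept in. The rest weighs less:

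- SAP 6.3 defines exclusion by reference to Protocol 7.3, which includes non-evaluability with an open list.
- The supposed choice between two doses is not in the text. A vomit-corrected dose would be an addition to the plan.
- The worry about a late decision carries little weight. Protocol 3.1 requires each subject's recovery during the trial to apply the release criteria, so recoveries are seen in any event. There is one arm and no hypothesis test for a late choice to influence.
- SAP 7.4 refers further detail to sponsor standards that are not available here, and some sections, such as Protocol 5.5.1.3, are blank in the public version. A rule may sit there.

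**Conclusion.** No change is needed. The visible text implies, without stating, that a subject replaced for vomiting is non-evaluable for fe. The plan supplies the means to exclude him, a forum to decide and a duty to show what was done. For the denominator, the literal reading is a single one: the syringe-weight dose, with vomit measured separately. Asking the sponsor to say whether and how would add detail without replacing an unsound rule by a better one.

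Keeping a subject with a large loss would matter in so small a group: 5.5 points on the faecal mean at a 50% loss (77.4 − 71.9), and more with two such subjects. That is the very case for which replacement and exclusion were provided. At 8 to 12 h, where no replacement is foreseen, the shift is at most 1.3 points for losses up to 10%. These sizes rest on assumed losses and CVs; the direction does not.

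The conclusion also rests on the analysis remaining descriptive, on individual values being listed, and on the meeting treating a replaced subject as Protocol 3.3.5 implies. Confidence is moderate, because the sponsor's PK standards could not be consulted.

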7.5 SECONDARY ENDPOINTS**7.5.1 Key secondary endpoint**

This section is not applicable as no key secondary endpoint has been specified in the CTP.

7.5.2 Secondary endpoints

Secondary PK endpoints will be assessed descriptively. This will be based on the PKS. The analysis of standard PK parameters is performed according to BI standards ([5](#)) [001-MCS-36-472_RD-01].

See [Section 7.4](#) of this TSAP for details regarding exclusion of PK parameters and plasma concentrations.

7.7 EXTENT OF EXPOSURE

Treatment exposure will only be listed by means of the date and time of drug administration.

7.8 SAFETY ANALYSIS

All safety analyses will be performed on the TS.

7.8.1 Adverse events

AEs will be coded with the most recent version of MedDRA.

The analyses of AEs will be descriptive in nature. All analyses of AEs will be based on the number of subjects with AEs and not on the number of AEs.

For analysis, multiple AE occurrence data on the electronic case report form (eCRF) will be collapsed into an AE event provided that all of the following applies:

- All AE attributes are identical (LLT, intensity, action taken, therapy required, seriousness, reason for seriousness, relationship, outcome, AESI)
- The occurrences were time-overlapping or time-adjacent (time-adjacency of two occurrences is given if the second occurrence started at most 1 hour after the first occurrence ended).

For further details on summarization of AE data, please refer to "Analysis and presentation of adverse event data from Clinical Trials" (8) and "Handling of missing and incomplete AE dates" (4).

The analysis of AEs will be based on the concept of treatment emergent AEs. That means that all AEs will be assigned to the screening or treatment phases as defined in [Section 6.1](#). AEs will be analysed based on actual treatments, as defined in [Table 6.1: 1](#).

An overall summary of AEs will be presented. This overall summary will comprise summary statistics for the class of other significant AEs according to ICH E3 and for the class of AESIs.

CTP: *The following are considered as AESIs:*

- *Hepatic injury*
A hepatic injury is defined by the following alterations of hepatic laboratory parameters:
 - *an elevation of AST (aspartate transaminase) and/or ALT (alanine transaminase) ≥ 3 -fold ULN combined with an elevation of total bilirubin ≥ 2 -fold ULN measured in the same blood sample, or*
 - *aminotransferase (ALT, and/or AST) elevations ≥ 10 fold ULN*
- *Severe infections (according to RCTC grading)*
- *Opportunistic and mycobacterium tuberculosis infections*

The investigator had to classify on the eCRF whether an observed AE was an AESI or not.

According to ICH E3 (9), AEs classified as 'other significant' need to be reported and will include those non-serious and non-significant AEs

- (i) which are marked haematological or other lab abnormalities, or
- (ii) which were reported with 'action taken with study treatment' other than 'dose not changed', or
- (iii) which lead to significant concomitant therapy as identified by the Clinical Monitor/Investigator at a Medical Quality Review Meeting.

The frequency of subjects with AEs will be summarised by treatment, primary system organ class and preferred term. AEs which were considered by the investigator to be drug related will be summarised separately. Separate tables will also be provided for subjects with SAEs, subjects with AESIs and subjects with other significant AEs (according to ICH E3 (9)). AEs will also be summarized by maximum intensity.

The system organ classes will be sorted by total frequency, preferred terms will be sorted by total frequency (within system organ class).

For disclosure of AE data on ClinicalTrials.gov, the frequency of subjects with non-serious AEs occurring with an incidence of greater than 5 % (in preferred terms) will be summarised by treatment, primary SOC and preferred term. The frequency of subjects with SAEs will also be summarised.

For disclosure of AE data in the EudraCT register, the frequency of AEs, the frequency of non-serious AEs with an incidence of greater than 5 % (in preferred terms) and the frequency of SAEs will be summarised.

For support of lay summaries, the frequency of subjects with drug-related SAEs will be summarised by treatment, primary system organ class and preferred term.

